### Estimating the Smallest Worthwhile Difference (SWD) of Antidepressants for Major Depressive Disorder: A Protocol

#### INTRODUCTION

Depression is the second leading cause of global disability (GBD 2019 Mental Disorders Collaborators, 2022) with point prevalence estimates upwards of 4.4% of the global population (WHO, 2017). Millions seek treatment for depression through antidepressant medications within the United States alone (Luo et al., 2020). Antidepressants are proven efficacious, backed by hundreds of randomized controlled trials and rigorous meta-analyses (Cipriani et al., 2018; Cuijpers et al., 2020). For instance, a network meta-analysis including 21 commonly prescribed antidepressants demonstrated an average standardized mean difference (SMD) of 0.30 (95% CrI = 0.26-0.34) favoring antidepressants over placebo (Cipriani et al., 2018). However, effect sizes such as SMDs in behavioral health research can miss the patient importance of an intervention (Furukawa et al., 2014). For instance, whether antidepressant treatments are a worthwhile option for patients, given the benefits in symptom improvement on the one hand and costs including harms, expenses, and other burdens on the other, remains controverted (Hengartner & Plöder, 2018; Kirsch & Sapirstein, 1998; Moncrieff, 2018).

The minimum important change (MIC), also known as the minimal important difference or minimal important clinical difference, is the smallest change in a health outcome that patients perceive as important (Jaeschke et al., 1989). Defining the MIC is a useful way to interpret patient-reported outcome measures (PROMs) (Carrasco-Labra et al., 2021). The MIC is often calculated through the anchor-based approach, which uses a readily interpretable external criterion to determine patients' importance of changes seen in a health outcome of interest. By definition, the MIC is specific to a particular assessment scale (Devji et al., 2020; Ferreira et al., 2012), generally lacks association with an intervention (McNamara et al., 2015), and does not explicitly account for costs and benefits relative to an alternative (Ferreira et al., 2012; McNamara et al., 2015). The MICs for depression scales have been estimated between a 7 to 9 point reduction for the Montgomery-Asberg Depression Rating Scale (MADRS) (Leucht et al., 2017), a 6 point reduction for the Beck Depression Inventory-II (BDI-II) (Hiroe et al., 2005), and a 7 to 8 point reduction for the Hamilton Depression Rating Scale 17-item version (HAM-D-17) (Furukawa et al., 2007; Leucht et al., 2013).

The MIC can thus help determine whether changes in health status are trivial or small but important from the viewpoint of the patients but does not relate to whether differences in changes in one treatment over another are worth the costs of the treatment including its harms, expenses, and other burdens. A conceptually different approach to facilitate interpretation of patient importance in PROM scores in the context of an intervention is to estimate the smallest worthwhile difference (SWD). The SWD is "the smallest beneficial effect of an intervention that justifies the costs, risks, and inconveniences of that intervention" over an alternative intervention including no treatment or placebo (Ferreira et al., 2012). The SWD represents a between-treatment assessment reflecting a trade-off of the benefits and costs of two treatment options (Furukawa, 2020). It is patient-derived, intervention-specific, and expressed as an absolute difference in outcomes between alternative treatments (Barrett et al., 2005, 2008; Ferreira et al., 2012; McNamara et al., 2015). Two methods have been proposed to estimate the SWD: the discrete choice experiment (DCE) and the benefit-harm trade-off method (BHTM). The DCE asks individuals to state their preferences for a series of hypothetical scenarios where attributes and their levels may vary (i.e., differing benefits and costs), which one then analyzes in multivariable regression models to determine the threshold for preference for one treatment over another (Franco et al., 2016). The BHTM asks individuals directly how many benefits they are willing to trade-off for the expected costs of an intervention over another (Barrett et al., 2005). The BHTM has been suggested as an easy-to-apply and useful method and has been used to estimate the SWD in treatments for respiratory disease (McNamara et al., 2015), fall prevention (Franco et al., 2016), and pain reduction therapies (Christiansen et al., 2018; Ferreira et al., 2013). Computer applications of the BHTM have also been successful at estimating SWDs when a treatment decision is to be made versus no treatment (McNamara et al., 2015).

[figure not shown]
Patient-centered medicine places greater value on the patient perspective (Devji et al., 2020; Laine & Davidoff, 1996). However, to our great surprise and dismay, the SWD of antidepressants for depression has never been estimated in over half a century of research into the psychopharmacology of depression. Identifying the SWD of antidepressants for depression would help understand patient expectations of antidepressant therapies, evaluate

the worthiness of the current antidepressants, and establish evidence-based benchmarks to be aimed at in clinical trials for new antidepressant therapies. The present study will therefore determine the SWD of commonly prescribed antidepressants for depressive disorders using the BHTO method.

## METHODS

### Participants

We will include respondents aged 18 and older, who reside in the USA, and are fluent in English. To improve data quality, it is suggested to use minimal inclusion criteria variables with panel survey samples, and to instead examine subgroup effects of the variables of interest (Chandler & Shapiro, 2016).

**Figure 1.** Subgroup combinations with primary interest of no current treatment (antidepressant or psychotherapy), positive screening for depressive symptoms, and no prior antidepressant treatment. Red boxes represent subgroups of interest with necessary minimum of  $n = 160$  to calculate subgroup smallest worthwhile difference, PHQ-9 = Personal Health Questionnaire 9-item, ATD = antidepressants, PT = psychotherapy, pop. = population.

Thus, salient factors that may influence respondent evaluations of the SWD will be accounted for in subgroup combinations based on 1) current treatment status (antidepressant or psychotherapy), current depression symptom status (PHQ-9), and antidepressant history. Figure 1 shows the subgroup combinations of interest.

Respondents will be recruited using Amazon's Mechanical Turk (MTurk). MTurk is an internet-based research crowdsourcing recruitment tool providing monetary compensation for participation. Potential respondents are called "MTurk Workers" and compose an established respondent pool. Researchers upload surveys through MTurk and request participation from workers fitting the inclusion criteria. High-quality data from demographically diverse populations can be drawn from the MTurk crowd with greater generalizability than internet or undergraduate convenience samples (Chandler & Shapiro, 2016). Psychometrics calculated with MTurk samples demonstrate effect sizes equal to standard sampling, high test-retest reliability, and high convergent and concurrent validity with state and trait psychological constructs (Chandler & Shapiro, 2016). For depression symptomology specifically, scores measured with the PHQ-9 were highly correlated ( $r = 0.78$ ) among MTurk respondents one week apart, suggesting adequate test-retest reliability (Carr, 2014).

In MTurk, workers are rated by researchers and given an approval rating for their trustworthiness. To increase data quality, we will restrict MTurk respondent enrollment to those with approval ratings above 95% (Paolacci & Chandler, 2014). Because of this restriction, surveys will not be modified with attention check validity questions. Attention is generally equivalent to other convenience samples and attention checks do not improve data quality for MTurk respondents with high approval ratings (Chandler & Shapiro, 2016). Respondents will provide e-consent and will be debriefed and compensated after completion. Compensation will be US\$1, which is commensurate with similar MTurk study lengths (Nikčević et al., 2020). The initial survey will be piloted with a small number of workers and feedback will be solicited before full survey deployment.

### Procedure

Participation is possible only after e-consent is signed (Supplement 2). We will collect the following information from respondents who give consent:

- *Demographic data:* Age, gender, race/ethnicity, education, employment, and insurance status
- *Clinical data:* lifetime diagnosed depression, current depressive symptoms (PHQ-9), family history of diagnosed depression, treatment preference (pharmacotherapy or psychotherapy), previous treatment (pharmacotherapy or psychotherapy) and current treatment (pharmacotherapy or psychotherapy)

### **Measurements**

Lifetime diagnosed depression will be determined with one yes/no question, “Have you ever been diagnosed with a depressive disorder by a healthcare professional?” Current depressive symptoms will be assessed with the Patient Health Questionnaire 9-Item (PHQ-9) (Kroenke et al., 2001). The PHQ-9 provides a good description of current depression severity: none-minimal (1–4 points), mild (5–9), moderate (10–14), moderately severe (15–19), and severe (20–27). The PHQ-9 is a reliable and valid instrument with good sensitivity (88%) and specificity (88%) for identifying major depression at a recommended cutoff of 9/10 (Kroenke & Spitzer, 2002). Family history of diagnosed depression will be determined with one yes/no question, “Has anyone in your family ever been diagnosed with a depressive disorder by a healthcare professional?” Treatment preference (pharmacotherapy or psychotherapy) will be determined with a two-option question, “If you were to receive treatment for depression, would you prefer drug or talk therapy?” Previous treatment (pharmacotherapy or psychotherapy) will be determined with a multiple-choice question, “Have you ever received treatment for depression (yes: drug therapy/pharmacotherapy, yes: talk therapy/psychotherapy, or no: I have never had treatment)?” Current treatment (pharmacotherapy or psychotherapy) will be determined with a multiple-choice question, “Are you currently receiving treatment for depression (yes: drug therapy/pharmacotherapy, yes: talk therapy/psychotherapy, or no: I am not currently receiving treatment)?”

The questionnaires will be implemented electronically using a dedicated electronic data capturing (EDC) system (Qualtrics) via MTurk. Only the system administrator has direct access to the server and back-ups. Researchers will have access to the MTurk worker ID which could be linked to personal information on Amazon public profile pages. This is dependent on respondents’ individual Amazon profile settings. Additionally, Amazon maintains access to individual MTurk IDs and personal information (i.e., social security number, IP address, bank account information). MTurk worker IDs are not shared outside the study team and will only be used for distributing remuneration. MTurk IDs will not be stored with survey responses/data. Worker IDs will be removed from the dataset after collection is completed and the stored dataset will be de-identified. Data will be retained on the Amazon servers per Amazon policy. Both Amazon and Qualtrics data will be deleted upon data collection completion and deidentification. The final deidentified dataset will be maintained on a local password-protected server in a locked room.

### **Obtaining the smallest worthwhile effect (SWD)**

The SWD will be estimated using the Benefit-Harm Trade-off Method (BHTM) (Barrett et al., 2005), presenting the survey respondents with variable, hypothetical magnitudes of antidepressant outcomes to find the smallest acceptable effect over natural recovery. The overall average smallest acceptable effect represents the SWD. Respondents will be asked a series of questions regarding the percentage of improvement they consider to be worthwhile, given the costs of antidepressant treatment. We will use the selective serotonin reuptake inhibitors (SSRIs) and serotonin-norepinephrine reuptake inhibitors (SNRIs) as the exemplar cases in the descriptions of antidepressants, as they are the most frequently prescribed (Luo et al., 2020), have similar efficacy and harm profiles (Cipriani et al., 2018), and are now mostly off-patent and hence similarly inexpensive.

The BHTM is a two-step method. In Step 1, respondents are presented with summaries of clinical depression, benefits, and costs (side effects, expenses, and burdens) associated with antidepressant treatment and with no treatment/natural recovery (see Supplement 2). The summaries will be piloted using two members of the Patient and Public Involvement (PPI) group at Oxford University. The patient members will review the scripts and provide valuable feedback as to the clarity, inclusivity, and accuracy of patient experiences captured by the descriptions. Respondents will be informed about how much improvement can be expected without antidepressant treatment, i.e., natural recovery. After the no-treatment comparison is established, respondents are presented with the potential costs of antidepressant treatment. They will be provided with a list of common (Trindade et al., 1998; U.S. Food and Drug Administration, 2019) and rare side effects (U.S. Food and Drug Administration, 2019).

In Step 2, respondents will determine if antidepressants are worthwhile given a hypothetical symptom reduction percentage compared to the known symptom reduction of natural recovery. They are asked to weigh the cost and benefits and asked if they would take the drug alternating between variable magnitudes of hypothetical

antidepressant outcomes. A detailed BHTM narrative and figures illustrating the variable antidepressant effects from the survey are provided in Supplement 2. There are two separate methods within the BHTM for determining the respondents' SWD; the *high-to-low* method and the *back-and-forth* method. We will randomly employ both methods because neither is shown to be more accurate or result in differential variance. The survey algorithm for both the high-to-low and back-and-forth methods are represented in Supplements 4.

### Sample Size

Sample size was calculated to achieve expected precision in the estimates of the SWD. Because there has been no study to estimate SWD for depression and its SD is unknown, we substituted it with the SD of SWD for pain also measured on a scale of 0-100: this study suggested an SD of 22 for SWDs of 20% (Ferreira et al., 2013). Assuming a similar SD, and to obtain a 95% confidence interval within 10 points, approximately 80 respondents per group are needed. We will also randomly assign participants to either the *high-to-low* or *back-and-forth* BHTM methods, which will require twice the respondents per method to determine differences between the methods with 160 respondents per group (80 respondents x 2 methods). Since we are estimating SWD and its 95% CI for 4 subgroups (see respondent recruitment above), 640 respondents are needed (160 respondents x 4 groups). This should be enough to examine all the pre-specified potential predictors (see Data analysis below) (Austin & Steyerberg, 2015).

The survey will be piloted with 300 respondents to determine if the population distribution estimate is appropriate to reach  $n = 160$  in all four subgroups. We have estimated that approximately 20% of the respondents will screen positive for moderate to severe depressive symptoms with the PHQ-9. This is greater than the general population, but still a conservative estimate for MTurk subgroups, which have been shown to demonstrate up to 3.6 times greater depression point prevalence than the general population (Ophir et al., 2020). Based on this estimated MTurk-specific subgroup populations, approximately 1,600 respondents may be necessary to reach 80 in the subgroups with the smallest populations (see Figure 1). If more respondents are needed, recruitment will continue until 80 people per subgroup are reached.

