**Supplement 5. Benefit-Harm Tradeoff Method Algorithm Testing and Sample Size Calculation**

We used two separate methods within the BHTM for determining the participants' SWD: the *high-to-low* method and the *back-and-forth* method (see Supplements 3 and 4). Both methods have been employed in the SWD literature (See Ferreira et al., 2012 and McNamara et al., 2015), and the most accurate SWD estimation had not been determined. Therefore, we opted to randomly allocated participants 1:1 to each method to see if they differed in their estimation. Our original sample size estimate for the SWD and its 95% CI for 4 clinical subgroups, required 780 participants based on population estimates. However, testing the difference between two separate methods required double the estimate. Based on subgroup populations, approximately N=1,600 participants were thought to be necessary to reach a minimum of n=80 in all 8 subgroups.

After we reached a minimum number of participants per group, we compared the SWD between methods. We found the difference between methods was 3.6 percentage points and we used 5 percentage point increments for the SWD. Thus, we determined both methods to be equally appropriate and all participants were analyzed together. Recruitment was stopped after all subgroups included n=80.

**Supplement 6.** Associations between demographic and clinical variables and SWD

	Univariable regression		Multivariable regression	
	Coefficient	95%CI	Coefficient	95% CI
Demographic Variables				
Age	0.050	-0.021 to 0.12	0.069	-0.03 to 0.16
Sex				
Male	ref		ref	
Female	-0.61	-2.75 to 1.53	-1.66	-4.01 to 0.67
Non-binary	1.66	-7.23 to 10.56	1.43	-7.75 to 10.61
Race				
White/Caucasian	ref		ref	
Black/African American	2.22	-2.53 to 6.97	3.57	-1.29 to 8.43
Asian	2.74	-2.40 to 7.89	3.33	-2.06 to 8.71
Latino/Hispanic	3.69	-1.98 to 9.35	6.55	0.62 to 12.47
Multiracial	2.27	-4.45 to 8.90	3.71	-3.00 to 10.42
Other	1.42	-8.86 to 11.70	0.90	-9.40 to 11.19
Education				
Less than high school	3.78	-2.36 to 9.92	2.61	-3.74 to 8.94
High school graduate/Equivalent	0.36	-2.96 to 3.69	0.04	-3.35 to 3.44
Some college	-0.61	-3.18 to 1.96	-1.16	-3.87 to 1.54
2-year degree	-3.23	-6.56 to 0.10	-2.76	-6.15 to 0.63
4-year degree	ref		ref	
Master's degree	-0.86	-4.45 to 2.73	-1.74	-5.34 to 1.86
Doctorate	-4.04	-11.25 to 3.17	-4.09	-11.26 to 3.08
Employment				
Disabled	3.62	-0.36 to 7.60	4.08	-0.23 to 8.40

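### The Sample Size section requires 160 respondents per clinical subgroup (80 per method), but its recruitment rule stops at 80 per subgroup, and Supplement 5 does not settle which unit applied

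*Combined protocol and SAP*

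**What the plan says.** The Sample Size section takes its SD from a pain study ("this study suggested an SD of 22 for SWDs of 20" percent) and derives the basic number from it: "Assuming a similar SD, and to obtain a 95% confidence interval within 10 points, approximately 80 respondents per group are needed". Because respondents are randomised to one of two questioning methods, it doubles this to "160 respondents per group (80 respondents x 2 methods") and multiplies by four clinical subgroups to reach 640. The 300-person pilot is there to check that 160 can be reached in all four. The Figure 1 caption, under Participants, also gives 160 as the minimum for each subgroup of interest.

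The same Sample Size paragraph that describes the pilot then changes number. It forecasts about 1,600 respondents in order to reach 80 in the smallest Figure 1 subgroups, and sets the rule: "If more respondents are needed, recruitment will continue until 80 people per subgroup are reached".

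Supplement 5 attaches the forecast of about 1,600 to a minimum of 80 in each of eight subgroups, confirms 1:1 allocation, and ends: "Recruitment was stopped after all subgroups included n=80". Supplement 2, which lists the changes from the protocol, does not mention the recruitment target.

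**The concern.** Within the Sample Size section, subgroup means one of the four clinical groups, and eight cells are never mentioned. On that wording the number required and the number at which recruitment may stop differ by a factor of two.

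The doubling was there so that each method could be read with the stated precision. If recruitment stops at half the number, that precision survives only when the two methods are pooled. The Data analysis section does not say what would be done if the methods disagreed, and Supplement 2 lists treating all responses alike among the changes from the protocol. So, as planned, the per-method numbers were a safeguard, and the literal rule removes it. A reader also cannot tell from the documents whether each clinical subgroup was meant to hold at least 80 or at least 160 people when recruitment closed.

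**Working it through.** **Inputs.** SD 22 on a 0–100 scale, a 95% interval within 10 points, 80 per group, two methods and four clinical subgroups (all Sample Size); 1:1 allocation (Supplement 5); comparison of the methods' total averages by t test (Data analysis). I use z = 1.96.

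**Reproducing the plan's figure.** If the target is a total width of 10 (half-width 5):

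n = (1.96 × 22 / 5)² = 8.624² = 74.4, so 75; solving with the t distribution gives 77.

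This agrees with the plan's approximate 80. At n = 80 the width is 2 × 1.96 × 22 / √80 = 86.24 / 8.944 = 9.6. The other possible reading, plus or minus 10, gives n = (1.96 × 22 / 10)² = 18.6, so 19, and cannot lead to 80. The target is therefore a total width of 10. The products 80 × 2 = 160 and 160 × 4 = 640 are exact.

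**Applying the two readings of the rule.** Width for one mean is 86.24 / √n. Width for the overall difference between methods is 86.24 × √(2 / n per method).

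| Meaning of 80 | Per clinical subgroup | Per method in a subgroup | Width, one method | Width, methods pooled | Width, overall method difference |
|---|---|---|---|---|---|
| per method within each clinical subgroup | 160 | 80 | 9.6 | 6.8 | 6.8 (320 v 320) |
| per clinical subgroup (literal) | 80 | 40 | 13.6 | 9.6 | 9.6 (160 v 160) |

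With t quantiles the one-method widths are 9.8 and 14.1. The last column takes every subgroup at its minimum; larger subgroups would narrow it.

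Under the literal rule the per-method interval is 13.6 / 9.6 = 1.41 times as wide as planned and misses the 10-point target. The pooled subgroup interval meets it.

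**The case against.** Three arguments stand against the concern.

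*The 80 was probably meant per cell.* Supplement 5 ties the forecast of 1,600 to eight subgroups of at least 80, which fits four clinical groups times two methods and so 160 per clinical group. It also gives 780 as the estimate before doubling, and 2 × 780 = 1,560 is close to 1,600. This is the likeliest intention. It does not mend the text: the Sample Size section links its 80 to the Figure 1 subgroups, Supplement 5 uses the same word for four groups and for eight, and its stopping sentence does not say which is meant.

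*No listed analysis loses its precision.* The Data analysis section plans an overall SWD, SWDs by subgroup and one overall comparison of methods. It lists no SWD per method within a clinical subgroup. With 80 per clinical subgroup, the pooled subgroup width is 9.6. This stands, and it limits the practical harm. But the Sample Size section sized the study per method, so its rule should agree with that.

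*The reported intervals point to more than 80.* In Supplement 6 the widest univariable contrast between clinical groups is −2.53 to 5.77, a half-width of (5.77 + 2.53) / 2 = 4.15. At SD 22 a group of 80 alone would contribute 1.96 × 22 / √80 = 4.82, so the smallest group would exceed (1.96 × 22 / 4.15)² = 108. The realised SD is not given. A group of 80 is ruled out down to an SD of about 4.15 × √80 / 1.96 = 18.9; below that the argument is inconclusive. Nor does a lower bound of 108 establish 160. It is evidence against a bare 80, not proof of the unit used.

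**Conclusion.** The inconsistency is real and can be read directly from the Sample Size section and the Figure 1 caption: 160 per clinical subgroup is required, and the rule stops at 80. Read literally, the rule gives a per-method width of 13.6 points against the stated 10, assuming SD 22, equal allocation and 10 points meaning total width. Pooled over methods, the width is 9.6.

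Two stronger conclusions are tempting and should not be drawn.

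- A reader might infer that recruitment in fact closed at half the target. The documents do not show this. Supplement 5 fits a target of 80 per cell, and its stopping sentence is compatible with either unit.
- A reader might infer that even 160 per subgroup is too few to compare the methods. The 10-point target was set for the SWD, and no precision target for the method difference is stated. The planned t test uses total averages, for which the width is 6.8 at 320 v 320 and 9.6 even at 160 v 160. No contrast of methods within a clinical subgroup is planned.

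The rule should be corrected because it governs when recruitment may end. The main subgroup estimates do not fall on it.

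**What to change.** - In Sample Size, restate the rule: recruitment continues until 80 respondents per method within each clinical subgroup, that is 160 per clinical subgroup, are reached. Bring the wording of the 1,600 forecast into line. If the protocol text is kept as a historical record, put the clarification in Supplement 2.
- In Supplement 5, say whether the closing 80 refers to four clinical subgroups or to eight subgroup-by-method cells, and give the number in each cell at stopping.
- If it was 80 per clinical subgroup, restate the planned precision as 9.6 points pooled over methods and 13.6 points per method, and log the departure from 160 in Supplement 2.
- State that the comparison of methods is the overall one in the Data analysis section, with a width of 6.8 points at 320 v 320 or 9.6 at 160 v 160, according to the unit used.

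The cost is wording and a table of counts. No respondents are added. The one drawback is that the stated per-method precision may turn out less favourable.
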